16. Previous involvement in contracting	X						
17. Relations with social services, HA and local providers	X						
18. Population Needs Assessment and use of research evidence for purchasing	X	X	X				
19. Comparison with HA Purchasing	Х		X				
20. Risk management	X		X				

¹ For direct administrative costs

5: ACTIVITY CHANGES AND SERVICE COSTS

5.1: CHANGES IN ACTIVITY IN SEVEN SERVICES

Lead: [name], Wessex Institute of Public Health Medicine

Main comparison: All TPP sites' activity versus activity in SFH and non-FH practices (ie rest

of population), before and after implementation of TP

Specific Hypotheses

The project brief identified seven services for monitoring before and after TP and in comparison with SFH populations. This section starts with hypotheses about the effects of TP on each of these services, which are summarised in Table 5.1. These hypotheses will be expanded to include those due to individual TP objectives which will be established in the first set of site visits. Annex 5 gives further details of the thinking behind each hypothesis.

Table 5.1

Hypotheses of Effects of TP on seven services
(to be supplemented by objectives of individual TPP sites)

Service	Hypotheses
Emergency Admissions ²	Reduction in emergency hospitalisation rates in total and in relation to specific conditions Reduction in length of stay, especially of long stay patients Shift in balance of acute/social care for specific groups (eg stroke) Changes in choice of providers at the margin
Maternity Services	Shift to more client-centred approach Shift to midwife (as opposed to consultant) assisted deliveries, depending on pricing policies Greater continuity of care Increase in home births

The term 'Emergency Admissions and A&E' as used in the project brief requires clarification since DHAs currently contract in very different ways for each of these. Emergency admissions are paid for per FCE depending on the form of the contract, while A&E is a host District funded service that is paid for by a simple block contract. Very little information is available on activity or costs in A&E. The degree to which emergency admissions are routed through A&E depends on local circumstances. The focus here is on emergency admissions which comprise the largest single aspect of TPP compared to standard fundholding. A&E is dealt with separately in the next section of the proposal.

Regional specialties	

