separate proposal and contract (not included in this proposal). The scope for using routine NHS data to monitor changes in the seven services discussed above is summarised in Table 5.2, which suggests that the routine data, notably the Hospital Episode Statistics (HES) in England, would provide valuable information in relation to three services: emergency admissions, maternity and regional specialties. HES can provide up-to-date data on all inpatient and day case episodes, along with demographic and clinical data. National HES data for 1993/4 along with regional data for 1994/5 and 1995/6 would be used to set baseline levels. Regional data would be used to monitor changes in each of these services. Members of the team have considerable expertise in such analysis at both regional and national level and are confident about being able to negotiate national HES through the National Casemix Office, as has been the case for other projects. (One of the team -[name] - works part time for the National Casemix Office.) Local HES data would be obtained via the TPP site/DHA. Preliminary consultations with Scottish Home and Health Department statisticians indicates that Scottish routine data are highly compatible with English HES and of higher quality. There should be no great difficulty producing an Anglo-Scottish analysis of activity trends. Routine data would have to be supplemented by collection of data at TPP level on use of non-NHS services. This could be obtained from TPP practice software for those sites reporting use of non-NHS services during the fieldwork described in the previous main section.

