Routine data, specifically HES, Community Korner and PACT data, would be of more limited use in the other four services, for which developments in information for contracting might also be expected (see Table 5.2). Both palliative care and mental health, which have growing elements of community and domiciliary care, are only partially captured by routine data, with its emphasis on NHS inpatient activity, leaving gaps regarding community service contacts with patients linked to diseases or to GPs. Although total community health service contacts are recorded, these cannot be linked to specific client groups or patients (the advent of the new computable NHS number will change this - the scope for its use by TPPs will be explored). Data on activity in both community health services and on health promotion are so weak that TPPs may choose to contract on the basis of staff inputs and/or clinics and sessions. For each of these services, routine NHS data would be supplemented by data from each TPP site, depending on how these data are specified by each in their contracting and monitoring arrangements.

Table 5.2
Routine data by topic and adequacy to detect changes in patterns of services

Service	Routine Data	Adequacy
Emergency Admissions	HES/SMR1	OK (all below omit private sector)
Maternity	HES/SMR1	ditto
Regional specialties	HES/SMR1	ditto
Palliative care	HES/SMR1 re NHS inpatients only	missing community service contacts to terminally ill
Mental illness	HES/SMR1 re NHS inpatients only, CPN contacts, PACT	missing community service contacts to mentally ill
Community services	contacts Staff numbers	no linkage to client groups
Health promotion	Clinics Staff numbers	ditto

HES diagnostic data has strict limitations. It is likely that it will only be possible to analyse trends in major diagnostic grouping or by ICD chapters.

Ideally, the analysis of routine data (eg HES/SMR1) would be undertaken for 1993/94, 1994/95, 1995/96 and 1996/97 as soon as possible after the end of March 1997 in order to contribute these analyses to the final report due at the end of September 1997. Unfortunately, there is likely to be a considerable lag in the availability of routine data. It could be October before a complete 1996/97 HES/SMR1 data set is available. Thus, it may not be possible to report on the changes in activity rates before the end of 1997.

Additional data to validate and interpret routine data

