- TPPs might be expected to change the balance of care purchased with substitution of community and social care for acute and perhaps vice versa, depending on the specific condition.
- 4. Changes might be expected in TPPs' choice of provider, again probably at the margin. A change in provider might be related to some or all of the above factors. However, the financial gains of withdrawal of all work from a particular provider may be offset for TPPs by the possibility of making a provider non-viable. Much closer relationships might be expected between provider management/clinicians and TPPs. Changes might also be expected in the locations of care settings, with a shift to more community or domiciliary settings if of demonstrated cost effectiveness.

Changes in each of these dimensions might be expected at the level of specialties and more so at the level of specific conditions. Specific hypotheses will be derived for all the major conditions leading to emergency admissions, based on the literature, including 30 NHS-E sponsored health needs assessment co-edited by one of the applicants ([name]), the Effectiveness Bulletins and other relevant literature.

Maternity Services

TPPs might be expected to involve the following changes:

- a shift to more client centred approach,
- a shift to midwife (as opposed to consultant) assisted deliveries, depending to some extent on pricing policies in contracts,

- 3. greater continuity of care, perhaps through purchase of packages of care with protocols,
- 4. an increase (perhaps) in the proportion of home births, depending on the views of the GPs involved.

Regional specialties

As no standard list of regional specialties exists, the following list of 8 services based on EL(93)98 will be used for convenience:

neurosurgery
cardiothoracic
spinal injuries
specialised paediatrics
neonatal intensive
medium secure units/challenging behaviour
renal
rehabilitation
genetics.

The effects of TP on each of these may be expected to vary, but broadly similar effects might be expected for the first seven which are services catering for relatively rare conditions. As few patients at TPP level might be expected to require these services, TPPs may want to explore the scope for more integrated purchasing, perhaps in conjunction with the DHA. Overall, changes similar to those applying to emergency admissions might be expected.

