Given the time-scale of the study, and the number of births that can be expected to accrue (see methods section below), it is not feasible to examine obstetric outcome or to ascertain women's experience of choice and continuity from service records alone. Thus women's perceptions of choice and control will be crucial. It will be important to establish whether women (including those from minority ethnic groups or with special needs) registered with EFHs or TPPs are more likely to feel they experienced:

- choice in the care they received (for example, choice of provider, choice of carer throughout the pregnancy and post partum period);
- continuity of care and carer (for example, how many different professionals were seen? Did women know the name of the lead professional responsible for planning and monitoring care? Did women know the person who cared for them during delivery? Did women receive conflicting advice?);
- control over the process of care (for example, did women feel fully informed about possibilities for place of birth? did they feel that every practical effort had been made to meet her wishes for place of birth? Did women carry their own case-notes and understand their content? Did women feel involved in decision about the pattern of postnatal care they received, including length of hospital stay and the number and timing of community visits?)
- satisfaction with the care they received (for example, were women satisfied with the quality of the information provided to them? With the quality of the communication between professionals?)

3. Women's experience of participation in the purchasing process

Do women's' experience of participation in the purchasing process differ according to whether care is commissioned and purchased by general practitioners or by Health Authorities?

Given the emphasis 'Changing Childbirth' placed on the incorporation of women's views into service plans and contracting it will be important to establish whether women registered with TPPs and EFHs, were more likely to feel:

- consulted in the development of purchasing plans and service specifications;
- their views were valued and incorporated into contracting documents.

4. Purchasing plans and contracts

1)0 purchasing plans and contracts differ if prepared by TPPs, EFHs and HAs?

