Specific (local) changes to the planned structure of services to meet contract specifications (in terms of what patterns of service delivery are proposed) will be elicited through telephone interviews with midwifery managers in provider trusts, and with general practitioners. Particular attention will be paid to planned resource distribution (for example extent of GP involvement, midwife substitution for obstetric or GP care). These telephone interviews will be undertaken in 1996 in relation to the 96/97 contracts and in 1997 in relation to the 97/98 contracts.

Resource Utilisation

The actual utilisation of resources by women will be elicited in two ways. Hospital Episode Statistics, although known to be flawed for maternity services, will provide some information about hospital based antenatal care, length of stay, number of admissions and methods of delivery. These will be examined for changes after the introduction of new contracts as well as for differences between patients registered at the different practices. However, postal surveys of women registered in each of the study practices at 3 months post-partum will provide most information on community antenatal and postnatal care (in particular, number of visits, with whom, how long and for which procedures). Participating practices will be asked to identify all women giving birth over a period of 17 months, starting in August 1996, for women having given birth in the previous May.

Assuming that participating EFHs. SFHs and NFHs will have an average list size of 10000, and that participation TPPs will have a combined list size of 20000, and assuming a birth rate of 4 per 1000, around 1700 births could be expected to accrue over the 17 month period.

Women's experiences of care and participation in the purchasing process

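### Section 5.1 rates HES/SMR1 adequate for maternity, but as the protocol describes that source it cannot test the all-site hypotheses on home births, continuity and client-centred care

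*Protocol*

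**What the plan says.** Section 5.1 plans to describe changes in seven services at all TPP sites, before and after total purchasing (TP), against SFH patients and against the district as a whole. For maternity:

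- **Hypotheses.** Table 5.1 lists four: a more client-centred approach, a shift to midwife-assisted deliveries, and "Greater continuity of care Increase in home births". Annexe 5 words the last as "an increase (perhaps) in the proportion of home births, depending on the views of the GPs involved".
- **Source.** Section 5.1 (Method) says HES and the other routine data "would provide valuable information in relation to three services: emergency admissions, maternity and regional specialties".
- **Coverage.** The same paragraph says "HES can provide up-to-date data on all inpatient and day case episodes", with demographic and clinical data attached.
- **Rating.** Table 5.2 grades each source on whether it can detect changed patterns of service. Emergency admissions with HES/SMR1 is graded "OK (all below omit private sector"), and maternity takes the same grade by ditto.

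The maternity proposal is more cautious. Under Resource Utilisation it writes: "Hospital Episode Statistics, although known to be flawed for maternity services, will provide some information about hospital based antenatal care". Under Women's experiences of maternity care it says that "it is not feasible to examine obstetric outcome or to ascertain women's experience of choice and continuity from service records alone".

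**The concern.** The adequacy rating and the hypotheses do not fit together. A home birth is neither an inpatient nor a day-case episode, so the source as described does not count it. The hypothesis in Annexe 5 is a proportion, which also needs the total number of births, and section 5.1 names no source for that total. Continuity and client-centred care are matters of who looked after a woman over the whole pregnancy and how she experienced it. Hospital episodes with demographic and clinical fields do not show this.

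Two consequences follow:

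- **A hypothesis reported from data that cannot show it.** A real rise in home births would appear in 5.1 only as fewer hospital deliveries.
- **Carry-over into section 5.2.** That section links 5.1 activity to unit costs, feeds the Efficiency Index and uses length of stay as a quality indicator. A birth moved home would register as lost activity, possibly as a saving, and would change the mix of women left in hospital. Moving care away from acute hospitals is part of the first question under the third objective, so this is not a side issue.

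**Working it through.** **1. Hypothesis against source (section 5.1 and Annexe 5)**

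| Table 5.1 maternity hypothesis | What it needs | Does HES, as described, hold it? |
|---|---|---|
| Home births | Births at home and all births | No: inpatient and day-case episodes only are described |
| Continuity | Carers across antenatal, delivery and postnatal care | No: hospital episodes only; the maternity proposal says women's experience of continuity is not obtainable from service records alone |
| Client-centred care | Women's experience | No, for the same reason in part (choice) |
| Midwife-assisted delivery | Hospital delivery detail | Not disputed here |

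**2. Consistency within Table 5.2.** For palliative care and mental illness the table restricts HES/SMR1 to NHS inpatients and flags missing community contacts. Maternity has an out-of-hospital element by its own hypothesis but carries no such flag.

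**3. Is there another all-site source in 5.1?** Three supplements are named: TPP-level data on non-NHS services; TPP-site data for the other four services; and additional data from sites and health commissions to validate and interpret the routine data. None is a birth count for TPP and comparator populations.

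**4. What the maternity study can supply.** Its own figure is reproduced first. Inputs (maternity proposal, Figure 1 and Resource Utilisation): 18 EFH, SFH and NFH practices with 10,000 patients each, 6 TPPs with 20,000 each, 4 births per 1000 per year, 17 months.

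- Patients: 18 × 10,000 + 6 × 20,000 = 300,000
- Births: 300,000 × 4/1000 × 17/12 = 1700, which matches the stated figure
- From TPPs: 120,000 × 4/1000 × 17/12 = 680
- From the other practices: 1700 − 680 = 1020

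All these births fall from May 1996 on, and the proposal states that a full before-and-after design is not feasible.

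**5. Size of the blind spot.** The home-birth shares below are assumptions; the documents give none. If the share moves from a to b with total births unchanged, the relative change in hospital deliveries is (1 − b)/(1 − a) − 1. It does not depend on the birth rate.

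| a to b | Change in hospital deliveries |
|---|---|
| 1% to 2% | −1.0% |
| 2% to 4% | −2.0% |
| 2% to 5% | 0.95/0.98 − 1 = −3.1% |
| 5% to 10% | −5.3% |
| 2% to 10% | 0.90/0.98 − 1 = −8.2% |

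Without a count of all births, none of these can be told from a fall in births.

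Case-mix: assume 15% of all births are operative, unchanged and all in hospital. The rate among hospital deliveries is 15/(100 − home %). At 2% home births it is 15.3%, at 5% it is 15.8%, and at 10% it is 16.7%.

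**6. Would subtraction do?** Take one 20,000-patient TPP at the protocol's 4 per 1000, so 80 births a year. Assume 2% at home (1.6 births) and 2% of hospital records missing (0.02 × 78.4 = 1.6). All births minus HES deliveries gives about 3.2, double the true count. Private deliveries, which Table 5.2 says are omitted, would inflate it further.

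**The case against.** The strongest reply has four parts.

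- **The protocol says what HES can provide, not what it leaves out.** Table 5.2 restricts HES/SMR1 to inpatients for two services but not for maternity, which might mean that maternity records reach further. A reader might infer from the concern that HES excludes home births as a fact. The documents do not say that, and it cannot be settled from them. This stands, and it is why documenting that HES/SMR1 captures home births would be an acceptable answer. The protocol does not currently make that statement.
- **Home births are followed elsewhere.** The maternity study asks whether EFHs and TPPs take part in or contract for more home births, has its practices identify every woman giving birth, and surveys the women. Core site visits cover maternity plans and later service changes, and Annexe 5 promises to monitor sites' own aims. So the tempting conclusion that home births cannot be assessed anywhere is wrong. None of this, however, gives a home-birth proportion before and after TP for all sites and comparators.
- **The rating is by service, and the hypothesis is modest.** Annexe 5 hedges it, and it is not a designated endpoint. This limits the weight of the point, but does not make the rating fit the hypotheses.
- **The maternity proposal's remarks prove less than they seem to.** A reader might take the remark on flaws to mean that HES is unfit for maternity. The proposal still uses HES for length of stay, admissions and method of delivery, and the remark does not mention home births. The statement about service records also rests on the time-scale and the number of births. Both are supporting evidence only.

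**Conclusion.** The point holds for section 5.1. On the protocol's own description of HES, the hypotheses on home births, continuity and client-centred care cannot be tested from the named source in the all-site before-and-after comparison, and no all-births denominator is named. The unqualified rating for maternity in Table 5.2 should not stand. The maternity study fills the gap only in part: 6 TPPs against 18 other practices, after the start of TP.

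The distortion is modest under the assumed shares: hospital deliveries down 1.0% to 8.2%, and an operative rate moving from 15.3% to between 15.8% and 16.7%. These figures are illustrative. They assume constant total births and, for the operative rate, that all operative births stay in hospital. The conclusion rests on coverage as described, not on these figures. HES remains usable for hospital maternity items.

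**What to change.** - **Table 5.2:** requalify maternity as hospital deliveries only, with home births and community maternity care not covered. Alternatively, document that HES/SMR1 captures home births.
- **Home births:** name a direct routine count of births by place of birth (for example birth notifications) for TPP and comparator populations, before and after TP. Do not derive home births by subtracting HES deliveries from all births.
- **Hospital delivery activity:** report it against all births.
- **If no such count can be obtained:** state that section 5.1 cannot test the home-birth hypothesis and that only the maternity study addresses it.
- **Continuity and client-centred care:** assign these to the maternity study, whose survey and interviews already cover much of this ground.

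The cost is one extra routine count and fewer maternity hypotheses claimed at all 53 sites.

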strong financial management and use of cost containment strategies (eg utilisation review, development of intermediate forms of care);

consistent local rules for sharing surpluses, coping with expensive cases, etc.

the size of the population base for 'insurance' purposes;

the level of capitation funding in relation to population need indicators and demands for care; availability of good data on activity, costs and quality from local providers:

access to independent evidence on cost-effectiveness of services and interventions;

an effective means of assessing the needs and views of their patients;

a feasible choice of providers over a range of services (including the possibility of new service providers and/or types of service);

a belief among GPs and other key stakeholders that, on balance, benefits of TP exceed costs; good relations between the pilot sites and the local health authority and local authority social services;

good relations with local clinicians;

creative use of the fund holding and other management allowances to cope with the additional work of TP;

the distribution of managerial work between the lead GPs in each practice involved in each site.

The second objective of the evaluation will be to discover whether TP generates additional transactions costs compared with health authority commissioning (see section 6, below). An important part of this will be to look at TPP contracting and whether it involves new forms of contracting or more detailed contract specification and monitoring. Another important consideration for the long term viability of TP concerns the distribution of transactions costs. If a high proportion of the costs fall on GPs who are able temporarily to absent themselves from their full clinical commitments, a question arises as to whether this is a generalisable model to be rolled out across the Service as a whole.

The third objective is to determine using a before-and-after method with concurrent controls the changes in activity, quality indicators and costs associated with passing the commissioning responsibility for a wider range of services to consortia of GP practices (see section 5, below). A number of questions will be looked at:

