Sites are in varying states of readiness. This means that the more advanced ones made changes associated with TP ahead of the April 1995 start date. Some sites will begin to act as genuine purchasers gradually throughout 1995-96, while others are likely to spend the whole of 1995-96 in preparation for purchasing in 1996-97. In addition, it must be remembered that HCHS purchasing and general practice/primary care are themselves undergoing significant changes and will continue to do so during the life of the evaluation.

All these features pose problems for design and interpretation of an evaluation. They indicate that some caution will have to be exercised in interpreting any changes which are observed as due to TP even when a controlled before-and-after design is adopted.

CHOICE OF COMPARISONS TO BE MADE

Parts of the study where data are available for all practices

For some aspects of the evaluation, all total purchasing sites will be studied. These include the nature of services being purchased, relationships with health commissions etc (see section 4, below). In these parts of the study, the unit of both data collection and analysis will be the site rather than the individual practice, although there will be limited opportunity to examine variation within sites. In relation to services purchased, comparisons in these areas will be able to be drawn between what the TP sites are doing, and what their host health commissions are doing on behalf of the patients of non TP practices.

For the routine data on referrals, admissions and length of stay (see section 5, below), the unit of analysis will be the individual practice. Certainly no attempt should be made to analyse by individual referring GP because these data are unreliable. Because data are available by practice, there will be an opportunity to analyse differences within sites and between sites as well as differences between TP sites and reference practices (see below). Use should be made of this opportunity, since within site variation may be large.

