The data will also enable a comparison to be made between the TP pilot sites' objectives and the extent to which these are realised in practice. A further comparison will be made between how the TP sites purchase, and the patterns of services which they purchase, and the policies and practices of the local health authority, FHSA or integrated health commission. Some of these data will provide the basis for more detailed work on specific services in selected TP sites and reference practices (eg for maternity services and mental health services). It will be important to explore how the health authority involves GPs and local communities in purchasing outside TP pilot sites. The final objective will be to monitor GPs' and other important participants' (eg TP managers') perceptions over time of the costs and benefits of involvement in a TP pilot.

METHOD

For a few of the 53 TP sites in this study, it may be possible to study nearly two years of commissioning of particular services; for others which were less fully prepared in April 1995, the period of purchasing is likely to be not much more than 12 months in 1996/97 preceded by a period of preparation in 1995/96. In all cases, it will be possible to see whether TP sites make an appreciable difference to the contracting process and the content of contracts even if the effects of such changes are not necessarily discernible in alterations in the pattern of care within the timescale of the research. Care will need to be taken to ensure, as far as possible, that changes at the sites which took place before the study began but in response to the prospect of TP can be identified (ie some practices may have begun to gear up for TP in 1994-95).

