A different perspective on the availability of services will also be sought from all the Provider units related to a sample of the Total Purchasing sites with and without a special interest in mental health and from GPMH sites. By means of telephone interviews with Clinical Directors followed where necessary by personal visits, the relative contributions of the different purchasing models to changes in the availability and configuration of services will be defined, comparing the start-up period with one year later.

Utilisation of services

Information about *utilisation* of services will be obtained from hospital in-patient episode databases, focusing on admission rates and length of stay for patients with diagnoses in ICD9 Chapter V who are registered with GPs in each Total Purchasing site, in GPMH practices, and also in each reference site. These data will be analysed for April 1995 to March 1996, and for April 1996 to March 1997. Information will be sought from the study sites about any action taken to reduce admissions and length of stay, e.g. the employment of nurses to visit the in-patient units to expedite discharge.

For out-patient referrals information will be sought from the relevant providers including practices and Community Mental Health Teams by means of available databases (including practice billing systems) and also through individual Community Psychiatric Nurse workload schedules in the sample of Total Purchasing, GPMH and reference sites selected for special study. This will depend on the availability of routine nursing data being available from existing sources. Reliable

outpatient information will be difficult to collect because of the wide variety of types of secondary mental health contact, and it will not be possible to determine how much out patient data will be collected until individual sites are visited. Changes in outpatient utilisation rates are not essential to this part of the study.

Needs assessment and information systems

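### Section 5.1 and mental-health Study 1 count 1995/96 as 'before' even at sites already purchasing that year, which pulls the before-after contrast towards zero at those sites

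*Protocol*

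**What the plan says.** Section 2 sets the design: "The third objective is to determine using a before-and-after method with concurrent controls the changes in activity, quality indicators and costs".

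Section 5.1, Method, fixes the 'before' by calendar for every site: "National HES data for 1993/4 along with regional data for 1994/5 and 1995/6 would be used to set baseline levels". Later in 5.1 the intended analysis years are listed one by one, from 1993/94 to 1996/97.

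The mental-health proposal, Study 1, under utilisation of services, covers admission rates and length of stay: "These data will be analysed for April 1995 to March 1996, and for April 1996 to March 1997". No earlier year is used there.

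On when exposure began, section 3 (the intervention and its context) says: "Some sites will begin to act as genuine purchasers gradually throughout 1995-96, while others are likely to spend the whole of 1995-96 in preparation". It adds that "the more advanced ones made changes associated with TP ahead of the April 1995 start date". Section 4, Method, says: "For a few of the 53 TP sites in this study, it may be possible to study nearly two years of commissioning of particular services". The same paragraph asks that changes made in expectation of TP be picked out, and names 1994-95 as a year in which some practices may have started.

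Section 2, under the fourth objective, says that nearly all sites start purchasing in April 1996, with 1995/96 spent preparing.

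**The concern.** A controlled before-and-after estimate needs a 'before' period free of the intervention. The protocol names the baseline years by calendar and says elsewhere that one of them contains real purchasing at some sites. For those sites 1995/96 is at least partly exposed time. Whatever TP had already achieved by then raises or lowers the baseline in the direction of the effect, and the before-after difference shrinks.

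The risk is a false finding of no effect, concentrated at the sites with the longest exposure. Study 1 is the more vulnerable, because no earlier year dilutes the error. The protocol asks for early changes to be identified and for caution in interpretation, but it gives no rule for classifying an early site's 1995/96 data.

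**Working it through.** **1. Is there a figure to reproduce?** Section 5.1 states no effect size, sample size or power. Study 1 states 80% power at 5% significance for psychiatric admissions per 1000 falling from 0.8 to 0.55 and from 0.4 to 0.3. These are falls of (0.8 − 0.55)/0.8 = 31% and (0.4 − 0.3)/0.4 = 25%, which agree with its description of a quarter to a third.

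**2. Formula.** Let δ be the TP effect in 1996/97, w the weight of a baseline year, p the share of sites already exposed in that year, and g the fraction of δ already present at those sites. With unexposed controls, the contrast estimates

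δ × (1 − Σ w·p·g), summed over baseline years.

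The protocol gives no p, g or w, so the values below are assumptions. They also assume an early effect in the same direction as the later one, and equal effects and weights across sites.

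**3. All-site share of the effect kept.**

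| p | g | A: 1995/96 alone, 1 − pg | B: three equal years, 1 − pg/3 | C: as B, with half as much in 1994/95, 1 − 1.5pg/3 |
|---|---|---|---|---|
| 5% | 0.5 | 97.5% | 99.2% | 98.8% |
| 5% | 1.0 | 95.0% | 98.3% | 97.5% |
| 10% | 0.5 | 95.0% | 98.3% | 97.5% |
| 10% | 1.0 | 90.0% | 96.7% | 95.0% |
| 25% | 0.5 | 87.5% | 95.8% | 93.8% |
| 25% | 1.0 | 75.0% | 91.7% | 87.5% |
| 40% | 0.5 | 80.0% | 93.3% | 90.0% |
| 40% | 1.0 | 60.0% | 86.7% | 80.0% |

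Column A is the Study 1 structure. Columns B and C illustrate 5.1. Of 53 sites, 5% is about 3, 10% about 5, 25% about 13 and 40% about 21. The lower rows of the table fit poorly with section 2's statement that nearly all sites start in April 1996.

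**4. At one early site (p = 1).**

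| g | A | B | C |
|---|---|---|---|
| 0.25 | 75% | 91.7% | 87.5% |
| 0.5 | 50% | 83.3% | 75% |
| 1.0 | 0% | 66.7% | 50% |

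Since purchasing is described as gradual, g = 1 is an upper bound.

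**5. What it could mean for Study 1's power.** The protocol does not say which contrast its power figure refers to. Suppose it is this one, with the standard error unchanged. Power of 80% corresponds to 1.96 + 0.84 = 2.80 standard errors.

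- 5% of the effect lost: 2.80 × 0.95 − 1.96 = 0.70, power about 76%.
- 10% lost: 2.80 × 0.90 − 1.96 = 0.56, power about 71%.

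These correspond to the two 10% rows in column A.

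**The case against.** Much can be said for the plan. For most sites 1995/96 is a legitimate pre-purchasing year and the one closest to follow-up. The protocol knows of the problem: section 3 advises caution even with controls, section 4 wants early changes identified, section 5.1 ties the reading of routine trends to site information, and Annexe 4 asks whether the site is already purchasing. Inpatient mental-illness data also fall within 5.1, so Study 1 is not the only mental-health series. All this stands and limits the likely size. It does not supply a rule. Nor is the matter simply one for an analysis plan, because the protocol itself names the years.

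Four stronger readings are tempting and are not supported:

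- *The three years are averaged, so the check for earlier divergence is lost.* The protocol does not say how they are combined. It lists four separate years and speaks of trends.
- *The remaining sites were changing services throughout 1995/96.* Section 3 describes them as preparing. It dates anticipatory change to before April 1995, at the more advanced sites.
- *Every site was live in 1995/96.* The community care proposal calls 1996/97 the second year of operation, which could suggest this, but sections 2 and 3 say otherwise.
- *1995/96 should be dropped for all sites.* That would discard a valid nearest year for most of them. It would also leave 1994/95, which the protocol itself flags for some practices, as half of the remaining baseline.

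**Conclusion.** The point holds for the early sites. Following the stated years counts exposed time as 'before' there and biases the contrast towards zero, provided the early effect has the same sign as the later one. The fault is clearest in Study 1, where 1995/96 is the whole baseline. In 5.1 the all-site bias is probably small. The tabulated cases with three equal years run from under 1% to about 13% lost, or up to 20% if 1994/95 is half as affected, and the high ends need more early sites than section 2 suggests. No figure here is an estimate: the number of early sites, how much effect they had by 1995/96 and the year weights are all assumed. It should be corrected, because the remedy is cheap and uses information the study already plans to collect.

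**What to change.** 1. From the site visits (Annexe 4, state of readiness for actual purchasing) and the later telephone interviews, date each site's first TP purchasing or TP-related change, by service where possible.
2. End that site's 'before' period at that date. Count its later 1995/96 data as exposed or as transition, decided before outcomes are examined. Keep 1995/96 as baseline for sites that start in April 1996.
3. Report TPP-minus-control differences for each of the four years already planned, so that divergence before TP is visible.
4. Add a sensitivity analysis with 1993/94 alone as baseline, since 1994/95 may also be affected. That year comes from national and not regional data, so it should be secondary.
5. Add earlier routine HES years to mental-health Study 1 and apply the same dating rule.

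The cost is a little more analysis, some extra routine data for Study 1, and fewer baseline observations at early sites. No new fieldwork is needed, provided the date is recorded along with purchasing status.
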